#### 4.8.3. Laboratory Data

Clinical laboratory values will be expressed using conventional SI units.

Laboratory parameters (haematology, biochemistry, bone turnover markers and urinalysis) will be summarised over the scheduled visits by treatment group. The actual value and change from baseline will be summarised for the haematology, biochemistry, urinalysis and bone turn-over parameters based on central laboratory measurements.

Urinalysis categorical parameters will be summarised using the number and percentage of patients within each category.

In addition, for haematology and biochemistry parameters, shift tables from baseline to each post-baseline value will be produced using the low/normal/high classification based on laboratory reference ranges. For some parameters with multiple reference ranges depending on menopausal status or menstrual cycle indicating in a comment variable, the one referenced to post-menopausal will be applied.

All laboratory data will be provided in data listings. Laboratory values outside the reference range will be identified in the subject listings.

A subset listing will be presented for all laboratory values with an overall abnormal clinically significant assessment. A listing for the description of abnormal assessments will be provided.

Urine pregnancy test data will be also presented in a listing.

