### **8.5 Safety endpoints**

- Change from baseline in clinical laboratory assessments
  - At Weeks 2, 4, 12 and 16 for haematology and urinalysis
  - At Weeks 2, 4, 8, 12 and 16 for clinical chemistry
- Change from baseline in vital signs (blood pressure, pulse rate, temperature) at Weeks 2, 4, 8, 12 and 16
- Change from baseline in weight, waist circumference and body mass index at Weeks 2, 4, 8, 12 and 16
- Proportion of subjects with clinically significant abnormal ECG findings at each visit
- Proportion of subjects with non-significant abnormal ECG findings at each visit
- Change from baseline at Weeks 2, 4, 8, 12 and 16 in ECG intervals (RR, PR, QT, QTc and QTcF)
- Proportion of subjects with maximum absolute QTcF values by category at each visit
  - $\leq 450$ ,  $>450$  to  $\leq 480$ ,  $>480$  to  $\leq 500$ ,  $>500$  msec
- Proportion of subjects with maximum change from baseline in ECG QTcF values by category at Weeks 2, 4, 8, 12 and 16
  - $\leq 0$ ,  $>0$  to  $\leq 30$ ,  $>30$  to  $\leq 60$ ,  $>60$  msec
- Change from baseline in the electronic Columbia Suicide Severity Rating Scale (eC-SSRS) at Weeks 4, 12 and 16
- Change from baseline to Weeks 12 and 16 in:
  - Serum concentration of bone-specific alkaline phosphatase (BALP)
  - Serum concentration of procollagen type 1 N-terminal propeptide (P1NP)
- Nature and severity of AEs
- Withdrawals due to an AE
- Use of concomitant medications

[figure not shown]

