### 11.10.2 Laboratory Parameters

Laboratory parameters (haematology, biochemistry, bone turnover markers and urinalysis) will be summarised over the scheduled visits by treatment group. Absolute values and changes from baseline will be summarised for the haematology, biochemistry and bone turn-over parameters. In addition, for haematology and biochemistry parameters, shift tables will be presented for changes in category (below, within or above normal range) from baseline to the subjects' worst post-baseline value ('worst' separately identified as either lowest or highest value observed on a subject for specific parameter being presented). Laboratory values outside the reference range will be identified in the subject listings.

A summary of abnormal clinically significant laboratory values will also be produced.

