### 2.5.3. Safety Variables

Safety assessments performed during the study included physical examinations, measurement of vital signs, 12-lead electrocardiograms (ECGs), clinical laboratory evaluations including hematology, serum chemistry, and urinalysis, and monitoring of adverse events.

The safety endpoints include:

- Change from baseline in clinical laboratory assessments:
  - ✓ At Weeks 2, 4, 12 and 16 for haematology and urinalysis
  - ✓ At Weeks 2, 4, 8, 12 and 16 for clinical chemistry
- Change from baseline in vital signs (blood pressure, pulse rate, temperature) at Weeks 2, 4, 8, 12 and 16
- Change from baseline in weight, waist circumference and body mass index at Weeks 2, 4, 8, 12 and 16
- Proportion of subjects with clinically significant abnormal ECG findings at each visit
- Proportion of subjects with non-significant abnormal ECG findings at each visit
- Change from baseline at Weeks 2, 4, 8, 12 and 16 in ECG intervals (RR, PR, QT, QTc and QTcF)
- Proportion of subjects with absolute QTcF values by category at each visit: <450, >450 to <480, >480 to <500, >500 msec
- Proportion of subjects with change from baseline in ECG QTcF values by category at Weeks 2, 4, 8, 12 and 16: <0, >0 to <30, >30 to <60, >60 msec
- Change from baseline in the electronic Columbia Suicide Severity Rating Scale (eC-SSRS) at Weeks 4, 12 and 16
- Change from baseline to Weeks 12 and 16 in:
  - Serum concentration of bone-specific alkaline phosphatase (BALP)
  - Serum concentration of procollagen type 1 N-terminal propeptide (PINP)
- Nature and severity of AEs
- Withdrawals due to an AE
- Use of concomitant medications

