**Table 2 Evaluation Intervals for Efficacy and Safety Analysis**

Evaluation	Targeted time point	Protocol-Specified Interval	Interval for Analysis
Screening Visit 1	Day -21	Day -21	Day -18 or earlier
Screening Visit 2*	Day -14	Day -16 to Day -12	Day -17 to Day -4
Baseline	Day 1	Day 1	Day -3 to Day 1
Week 2	Day 15	Day 12 to Day 18	Day 2 to Day 22
Week 4	Day 29	Day 26 to Day 32	Day 23 to Day 43
Week 8	Day 57	Day 53 to Day 61	Day 44 to Day 71
Week 12	Day 85	Day 81 to Day 89	Day 72 to Day 99
Week 16 FU	Day 113	Day 108 to Day 118	Day 100 or later

\* At least 6 days after Screening Visit 1 to allow at least 6 days of paper diary data to be completed. Study day is calculated per section 4.2.8.

In case more than one measurement per time period is captured, the closest to the targeted time point will be considered for analysis. If two measurements occur at the same distance from the target day for a particular analysis window then the first measurement will be considered for analysis. Unscheduled visits will be taken into account. In case of withdrawal, all data from the early termination visit will be assigned under its corresponding analysis visit according to its day.

Actual dates and times will be used for pharmacokinetic summaries rather than nominal days and times.

Any visits occurring outside visit windows defined in the protocol should be recorded as a PD and will be reviewed at the BDRM to assess on an individual case by case basis to which visit the data should be allocated.

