Table 14.2.14.1	Mean Daily Frequency of Moderate and Severe Hot Flushes and Change From Baseline by Week and by Region (Full Analysis Set)
Table 14.2.14.2	Mean Weekly Severity of Moderate and Severe Hot Flushes and Change From Baseline by Week and by Region (Full Analysis Set)

*Displays of Adverse Events (CSR Section 14.3.1)*

Table 14.3.1.1	Overview of Treatment-Emergent Adverse Events (TEAE) (Safety Analysis Set)
Table 14.3.1.2	Treatment-Emergent Adverse Events (TEAE) by System Organ Class and Preferred Term (Safety Analysis Set)
Table 14.3.1.3	Serious Treatment-Emergent Adverse Events (TEAE) by System Organ Class and Preferred Term (Safety Analysis Set)
Table 14.3.1.4	Drug-Related Treatment-Emergent Adverse Events (TEAE) by System Organ Class and Preferred Term (Safety Analysis Set)
Table 14.3.1.5	Treatment-Emergent Adverse Events (TEAE) Leading to Treatment Discontinuation by System Organ Class and Preferred Term (Safety Analysis Set)

Table 14.3.1.6	Treatment-Emergent Adverse Events (TEAE) Leading to Study Discontinuation by System Organ Class and Preferred Term (Safety Analysis Set)
Table 14.3.1.7	Treatment-Emergent Adverse Events (TEAE) by System Organ Class, by Preferred Term and by Severity (Safety Analysis Set)
Table 14.3.1.8	Treatment-Emergent Adverse Events (TEAE) by System Organ Class, by Preferred Term and by Relationship to Study Treatment (Safety Analysis Set)

*Other Safety Information (CSR Section 14.4)*

Table 14.4.1.1	Clinical Laboratories: Hematology Actual Values and Changes Over Time on Study (Safety Analysis Set)
Table 14.4.1.2	Clinical Laboratories: Biochemistry Actual Values and Changes Over Time on Study (Safety Analysis Set)
Table 14.4.1.3	Clinical Laboratories: Bone Turnover Markers Actual Values and Changes Over Time on Study (Safety Analysis Set)
Table 14.4.1.4	Clinical Laboratories: Urinalysis Actual Values and Changes Over Time on Study (Safety Analysis Set)
Table 14.4.1.5	Clinical Laboratories: Urinalysis Categorical Actual Values Over Time on Study (Safety Analysis Set)
Table 14.4.2.1	Clinical Laboratories: Shifts from Baseline Versus Each Post-Baseline Visit for Hematology (Safety Analysis Set)
Table 14.4.2.2	Clinical Laboratories: Shifts from Baseline Versus Each Post-Baseline Visit for Biochemistry (Safety Analysis Set)
Table 14.4.3	Vital Signs: Actual Values and Changes Over Time on Study (Safety Analysis Set)

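### The SAP omits the protocol's worst-post-baseline laboratory shift tables, tabulates one closest-to-target value per visit instead, and declares no change

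*SAP*

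**What the plan says.** **Laboratory shifts.** Protocol section 11.10.2 states that for haematology and biochemistry "shift tables will be presented for changes in category (below, within or above normal range) from baseline" to each subject's "worst post-baseline value ('worst' separately identified as either lowest or highest value observed on a subject" for the parameter concerned. SAP section 4.8.3 states that "shift tables from baseline to each post-baseline value will be produced using the low/normal/high classification based on laboratory reference ranges". The list of tables in SAP section 7.1 settles what is meant (Table 14.4.2.1 is titled "Clinical Laboratories: Shifts from Baseline Versus Each Post-Baseline Visit for Hematology (Safety Analysis Set"), and Table 14.4.2.2 does the same for biochemistry. No table to the lowest or highest post-baseline value is listed.

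**Selection of values.** SAP section 4.2.12 applies its analysis windows to safety data as well as to non-diary efficacy data. Under Table 2: "In case more than one measurement per time period is captured, the closest to the targeted time point will be considered for analysis". Ties go to the earlier measurement. Unscheduled visits compete in the same windows, and early-termination data are assigned by study day. There is no exception for extreme values.

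**QTcF.** Protocol section 8.5 lists "Proportion of subjects with maximum absolute QTcF values by category at each visit" and "Proportion of subjects with maximum change from baseline in ECG QTcF values by category at Weeks 2, 4, 8, 12 and 16". SAP section 2.5.3 has "Proportion of subjects with absolute QTcF values by category at each visit". The SAP's change-from-baseline endpoint also loses the word maximum, and SAP section 4.8.5 summarises both by time point.

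**Declaration.** Protocol section 11.4 requires any departure from a protocol-specified analysis to be documented in an amendment or in the SAP. SAP section 5 reports that there are none.

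**The concern.** Safety and tolerability is one of the two primary objectives (protocol section 6.1). A worst-value shift table answers a simple question for each dose: how many women who were normal at baseline were ever low or ever high on treatment? By-visit tables answer a different one: how many were low or high at this visit, on the value selected for it? Transient abnormalities at different visits, or found on repeat sampling, are what the first table collects and the second scatters or leaves out. The loss bears on dose comparison, because SAP section 4.3 bases the interim safety review on adverse events and withdrawals. The final tables are thus the main grouped view of the laboratory values. Since section 5 says nothing has changed, a reader of the study report would not know that a protocol table is missing.

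**Working it through.** The plan gives no figure to reproduce here. The check compares the texts, asks what by-visit tables can recover, and applies the window rule to assumed measurements.

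**1. Can the protocol's count be recovered from by-visit tables?** Let n_v be the number of subjects in a dose group shifting to high at visit v, and E the number who ever shift to high. If every value is tabulated, all that follows is

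max(n_v) ≤ E ≤ sum of n_v.

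Take 30 per group (the 30 x 5 of protocol section 11.1.1) and assume one high shift at each visit.
- Chemistry, five post-baseline visits (Weeks 2, 4, 8, 12, 16): E lies between 1 and 5, that is 1/30 = 3.3% to 5/30 = 16.7%.
- Haematology, four post-baseline visits (none at Week 8): E lies between 1 and 4, that is 3.3% to 4/30 = 13.3%.

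One persistently high subject and several transiently high subjects give the same by-visit tables. This needs no extra samples. If extreme values are dropped by the window rule, even the upper bound fails.

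**2. When does a value drop out?** Inputs are the analysis intervals in SAP Table 2: Week 2, Days 2-22, target 15; Week 4, Days 23-43, target 29; Week 8, Days 44-71, target 57; Week 12, Days 72-99, target 85.

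Assumed chemistry values: Day 15 = 30, Day 29 = 35, unscheduled Day 36 = 160, Day 57 = 40, Day 85 = 33, Day 113 = 30. Day 36 is in the Week 4 window, |36 − 29| = 7 days from target, against 0 for Day 29. The rule selects Days 15, 29, 57, 85 and 113. The largest tabulated value is 40; the 160 is in no by-visit laboratory table.

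Days on which one extra measurement would lose to the scheduled one:
- Scheduled visits on target: 20 + 20 + 27 + 27 = 94 of 94 possible days.
- Scheduled visits at the late edge of the protocol window (Days 18, 32, 61, 89): 14 + 14 + 19 + 19 = 66 of 94 (70%).
- Haematology, leaving out the Week 8 window: 20 + 20 + 27 = 67 of 67 on target, and 14 + 14 + 19 = 47 of 67 (70%) at the late edge.

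These shares are conditional on an extra sample existing. The documents do not say how often one will.

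**3. Early termination.** This visit includes chemistry, haematology and ECG (protocol section 8.6.7). If earlier visits fell on target, an early-termination chemistry or ECG result on Days 16-22, 30-43 or 58-71 loses to the visit already in its window: 7 + 14 + 14 = 35 of the 69 days from Day 16 to Day 84. For haematology, with no Week 8 sample, the count is 7 + 14 = 21 of 69.

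**4. QTcF.** The protocol's maximum is taken at each visit, and the schedule shows one ECG entry per visit. With one ECG in a window, the maximum is that value and nothing changes. With two, it can: assume 440 msec on Day 29 and 505 msec on Day 36, with 430, 445, 438 and 430 msec on Days 15, 57, 85 and 113. The SAP tabulates 440 at Week 4, and the subject is never counted above 450. A within-window maximum gives 505 at Week 4, in the category above 500.

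**The case against.** Several points on the other side stand.

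- **Nothing is lost from the data.** SAP section 4.8.3 lists all laboratory values, flags those out of range, and adds a listing of clinically significant abnormalities. All ECG data are listed too.
- **Clinically significant findings are counted.** Protocol sections 10.3.3, 10.3.5 and 10.3.6 require them to be reported as adverse events. SAP section 4.8.2 counts each subject once per preferred term, at the highest severity, whatever the visit window. A reader might infer that a worst value can disappear from every table; the documents do not support that. What can be missing is the numeric value, and any out-of-range result not judged clinically significant.
- **Displacement needs at least two measurements in one window.** The protocol schedules no repeats, and its section 10.1 mentions unscheduled draws only as a possibility. Choosing the value closest to target is ordinary practice for by-visit summaries.
- **The QTcF wording is limited.** A reader might infer that the protocol promised one on-study maximum QTcF table. It did not: sections 8.5 and the synopsis say at each visit or at named weeks, and section 11.10.4 specifies no maximum analysis.
- **No dilution factor can be given.** A reader might divide an event rate by the number of visits to size the loss. The documents give no rate of transient abnormalities, and the visit count differs between chemistry and haematology.

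One could also read the SAP's reference to each post-baseline value as covering every measurement. The table titles and the window rule point the other way.

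None of this supplies the missing count. Listings give no totals by dose group, and the adverse event route depends on the investigator's judgement of significance.

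**Conclusion.** The point holds for the laboratory tables. The protocol specifies shifts to the lowest and highest post-baseline value; the SAP omits them and states that nothing has changed. The per-group number of subjects ever shifting low or high cannot be read from what is planned. With one shift per visit and 30 per group, the range left open is 3.3% to 16.7% for chemistry and 3.3% to 13.3% for haematology. Those ranges are illustrations under assumed counts, not estimates. Complete absence of an extreme value from the laboratory tables is a further, conditional loss, needing an unscheduled, repeat or early-termination value beside a nearer one.

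For QTcF the departure is narrow: the within-visit maximum is gone, with an effect only where a window holds more than one ECG.

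Safety summaries are descriptive, and SAP section 4.3 does not list laboratory or ECG data in the interim safety review. This is therefore a reporting gap and an inaccurate declaration. It does not threaten the efficacy inference.

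**What to change.** 1. Add to SAP sections 4.8.3 and 7.1 the protocol's shift tables for haematology and biochemistry: baseline category against lowest, and against highest, post-baseline value. State that all post-baseline values count, including unscheduled, repeat and early-termination ones; protocol section 11.10.2 does not spell this out. Keep the by-visit tables.
2. In SAP sections 2.5.3 and 4.8.5, use the maximum QTcF and the maximum change from baseline within each visit window for the category tables.
3. Correct SAP section 5. If the sponsor prefers by-visit shifts only, section 5 should say so and give the reason.

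A single table of on-study maximum QTcF and maximum change would be a cheap optional addition, not a restoration of a protocol table.

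The cost is a few sentences and a small number of extra tables. No new data are needed.

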**Table 4 List of Laboratory Parameters**

Category	Parameters
Haematology	red blood cell (RBC) count, white blood cell (WBC) count, haematocrit, haemoglobin, MCV, platelet count and WBC differentials

---

Biochemistry	sodium, potassium, glucose, urea (blood urea nitrogen), creatinine, creatine kinase, albumin, calcium, phosphate, bilirubin (total), alkaline phosphatase, aspartate transaminase (AST), alanine transaminase (ALT), gamma glutamyl transferase (GGT), bicarbonate, magnesium, chloride, total protein, haemoglobin A1c (HbA1c)
Urinalysis	glucose, bilirubin, ketones, specific gravity, blood, pH, protein, urobilinogen, nitrites, leucocyte esterase, sedimentation
Bone Turnover Markers	bone-specific alkaline phosphatase (BALP) and procollagen type 1 N-terminal pro-peptide (PINP)

---

#### 4.8.4. Vital Signs and Physical Examinations

Vital signs parameters include weight (kg), BMI, heart rate (beat/min, (bpm)), systolic and diastolic blood pressure (mmHg), waist circumference (cm) and temperature (°C).

The following conversions will be applied:

$$\text{Weight (kg)} = 0,45359237 * \text{Weight (lb)}$$

$$\text{Waist circumference (cm)} = 2,54 * \text{Waist circumference (Inches)}$$

$$\text{Temperature (°C)} = (\text{Temperature (°F)} - 32) / 1.8$$

The actual value and change from Baseline will be summarised descriptively by treatment group and time point for vital signs parameters.

By-subject listings of vital sign measurements will be presented. A listing for the description of abnormal assessments will be provided.

Physical examination includes a review of the following body systems: General appearance, Skin, Head, eyes, ears, nose and throat, Respiratory, Cardiovascular, Abdomen (including liver and kidneys), Musculoskeletal and Neurological. All physical examination findings will be presented in a data listing.

#### 4.8.5. Electrocardiogram

ECG interval parameters include RR interval (msec), PR interval (msec), QT interval (msec), QTc interval (msec) and QTcF interval (msec).

QTcF interval will be derived using:  $QT \text{ interval} / (RR \text{ interval})^{1/3}$

The actual value and change from Baseline will be summarised descriptively by treatment group and time point for ECG parameters.

The proportion of subjects with absolute QTcF values by category below will be summarized by time point for the following categories:  $\leq 450$ ,  $>450$  to  $\leq 480$ ,  $>480$  to  $\leq 500$ ,  $>500$  msec.

Similarly, the proportion of subjects with an increase from baseline in QTcF values will be summarized by time point for the following categories:  $\leq 0$ ,  $>0$  to  $\leq 30$ ,  $>30$  to  $\leq 60$ ,  $>60$  msec.

ECG Overall interpretation (normal, abnormal clinically and not clinically significant results) will be summarized at baseline and each study visit.

All ECG data for each subject will be provided in data listings. A listing for the description of abnormal assessments will be provided.

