Table 14.4.4.1	Electrocardiogram Interval Results: Actual Values and Changes Over Time on Study (Safety Analysis Set)
Table 14.4.4.2	Electrocardiogram Results: QTcF Categorical Actual Values and Changes Over Time on Study (Safety Analysis Set)

Table 14.4.4.3	Summary of ECG Overall Interpretation by Visit (Safety Analysis Set)
Table 14.4.5.1	Electronic Columbia Suicide Severity Rating Scale Categories Values Over Time on Study (Safety Analysis Set)
Table 14.4.5.2	Electronic Columbia Suicide Severity Rating Scale: Shifts from Baseline Versus Post-Baseline for Suicidal Ideation Scores (Safety Analysis Set)
Table 14.4.6	Prior Medications (Safety Analysis Set)
Table 14.4.7	Concomitant Medications (Safety Analysis Set)

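### SAP 4.8.5 gives RR in msec but divides QT by the cube root of RR with no conversion to seconds, so QTcF programmed as written is one tenth of its msec value

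*SAP*

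**What the plan says.** SAP 4.8.5 (Electrocardiogram) first lists the parameters and their units: "ECG interval parameters include RR interval (msec), PR interval (msec), QT interval (msec), QTc interval (msec) and QTcF interval (msec"). The derivation follows directly. "QTcF interval will be derived using" introduces the formula QT interval / (RR interval)^(1/3), which carries no unit or scaling factor.

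The section then puts the result into categories. For actual values, "The proportion of subjects with absolute QTcF values by category below will be summarized by time point", with cut-points at 450, 480 and 500 msec. For changes, "the proportion of subjects with an increase from baseline in QTcF values will be summarized by time point", with cut-points at 0, 30 and 60 msec. The output is Table 14.4.4.2 in SAP 7.1, titled "Electrocardiogram Results: QTcF Categorical Actual Values and Changes Over Time on Study (Safety Analysis Set").

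These categories are a named safety endpoint. Protocol 8.5 has "Proportion of subjects with maximum absolute QTcF values by category at each visit", and SAP 2.5.3 has "Proportion of subjects with absolute QTcF values by category at each visit". Both sections name RR without a unit. Neither document gives another QTcF formula, another unit for RR, or a conversion of RR. By contrast, SAP 4.8.4, immediately before, says "The following conversions will be applied" and writes out the rules for weight, waist circumference and temperature.

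**The concern.** The unit list, the formula and the category cut-points in SAP 4.8.5 cannot all be right together. QT in msec divided by the cube root of RR in msec does not give a value in msec, and the result cannot reach the section's own cut-points.

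At stake is the QTcF safety summary. If the formula is programmed literally, the categorical table would look like a clean result: nobody above 450 msec and no increase above 30 msec. The QTcF rows of Table 14.4.4.1 would be ten times too small. Two programmers working independently from the same text could agree on the wrong number, and neither document specifies a check against a machine-recorded QTcF.

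ECG outputs have some importance in this programme. Protocol 5.1.3 names a possible effect on cardiac rhythm as the only potential safety signal in the healthy-volunteer studies. It adds that the arrhythmias were probably coincidental and that later Holter monitoring in RELENT-1 found no treatment effect. Protocol 5.1.1 reports no hERG inhibition. So there is no known QT problem, but the specification of these tables should be unambiguous.

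**Working it through.** **Inputs from SAP 4.8.5**
- Units: RR, QT and QTcF all in msec.
- Formula: QTcF = QT / RR^(1/3).
- Cut-points: 450, 480 and 500 msec for actual values; 0, 30 and 60 msec for change.

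The plan gives no worked QTcF value to reproduce. The QT and RR values below are illustrative assumptions and do not come from the documents.

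**Scale factor**

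RR (msec) = 1000 × RR (s), and 1000^(1/3) = 10. Hence

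QT / [RR (msec)]^(1/3) = QT / {10 × [RR (s)]^(1/3)} = (1/10) × QT / [RR (s)]^(1/3).

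The factor is exactly 1/10 for any QT and RR. A numerical check over QT 360 to 520 msec and RR 600 to 1200 msec gave a ratio of 0.1 at every point.

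**Actual values (msec)**

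| QT | RR | As written, RR in msec | RR in seconds | Class as written | Class with RR in seconds |
|---|---|---|---|---|---|
| 400 | 600 | 47.4 | 474.3 | ≤450 | >450 to ≤480 |
| 400 | 800 | 43.1 | 430.9 | ≤450 | ≤450 |
| 400 | 1000 | 40.0 | 400.0 | ≤450 | ≤450 |
| 400 | 1200 | 37.6 | 376.4 | ≤450 | ≤450 |
| 480 | 800 | 51.7 | 517.1 | ≤450 | >500 |

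**Change from baseline**

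Take a QT rise from 400 to 460 msec at RR 800 msec.
- As written: (460 − 400) / 800^(1/3) = 6.5, class >0 to ≤30.
- RR in seconds: (460 − 400) / 0.8^(1/3) = 64.6, class >60.

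**What the cut-points become**

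Multiplying by 10, the as-written cut-points of 450, 480 and 500 correspond to a true QTcF of 4500, 4800 and 5000 msec. The change cut-points of 30 and 60 correspond to true rises of 300 and 600 msec. In terms of QT, exceeding 450 as written needs about 450 × 600^(1/3) = 3795 msec at RR 600, or 450 × 10 = 4500 msec at RR 1000. No plausible record gets there. Only the split at 0 survives, because dividing by 10 does not alter the sign of a change.

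**The case against.** The best reply is that this is an omitted unit and not a miscalculated figure. The msec labels belong to the list of reported parameters, the formula line has no unit, and the output scale and cut-points show that RR in seconds must be meant. A competent programmer would convert. If one did not, a QTcF near 43 beside a QT near 400 would stand out in the summary of actual values (Table 14.4.4.1) and in the by-subject ECG listing. That is fair, and it makes a literal error in the final tables unlikely. It does not make the text right: a programmer or validator has an explicit unit and an explicit formula, and together they give the wrong scale.

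The reach is also limited. Under SAP 4.3 and 4.3.3 the interim safety review uses adverse events and early withdrawals, so decisions on doses and randomisation ratios do not rest on derived QTcF. Safety endpoints are not tested (protocol 11.10). The investigator judges ECG significance and reports clinically significant findings as adverse events (protocol 10.3.3). These points stand and lower the weight.

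Two further points also stand. The unit in which RR is collected may be in the annotated CRF that the SAP cites but that is not available here. If RR were stored in seconds, the formula would work and the msec label would be the error; one of the two lines needs correcting either way. Also, SAP 3.1 and 4.6.2.7 describe the blinded data review in the past tense, so programming may already be done. The request is therefore to check the program as well as the text. The contrast with the conversions in SAP 4.8.4 is only supporting evidence, since those turn collected units into reporting units and are not scaling inside a derived formula.

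**Conclusion.** The concern holds. The formula in SAP 4.8.5 with the unit stated there gives exactly one tenth of QTcF in msec, and nothing elsewhere in the protocol or SAP corrects it. Followed literally, it would put every plausible record in the lowest QTcF class and leave the >30 and >60 msec change classes practically empty.

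The factor of ten is exact and rests on no assumption about QT or RR. The effect on the tables is conditional on literal programming, which the documents neither show nor rule out. It is confined to derived QTcF in descriptive end-of-study outputs. Raw QT, the investigator's interpretation (Table 14.4.4.3), the interim decisions and all efficacy analyses are unaffected. QTc is listed separately and the SAP gives no derivation for it. The correction should be made, but it does not threaten the trial's main conclusions.

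**What to change.** Replace the derivation in SAP 4.8.5 with: QTcF (msec) = QT (msec) / (RR (msec)/1000)^(1/3). Confirm the unit in which RR is stored and that the program line does this. If a machine-recorded QTcF is collected, compare the derived values with it. The cost is one line of SAP text and a check of one program line. Data collection does not change.
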